### Duration of stable disease

Stable disease is measured from the start of the treatment until the criteria for progression are met, taking as reference the smallest measurements recorded since the treatment started.

### Progression-Free Survival

Progression-free survival (PFS) is defined as the duration of time from start of treatment to time of progression or death, whichever occurs first.

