### 2.3 Secondary Objective(s) and Endpoint(s)

Secondary Objective	Endpoint(s)	Time Frame
1. To assess duration of response (DOR) 24-week landmark progression-free survival (PFS:24)	DOR (CR+PR)	From initiation of study treatment to time of progression or death, whichever occurs first, assessed up to 24 weeks
2. Median PFS and overall survival (OS)	
 
• Median PFS
 
• overall survival (OS)
 
	From initiation of study treatment to the time of death from any cause on study, assessed up to 48 months
3. Tumor responses will also be calculated by Immune Related Response-Criteria (irRC)	Tumor responses (irRC)	Through study completion, assessed up to 24 months

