**Table 5.1 Trial Treatment**

Drug	Dose/ Potency	Dose Frequency	Route of Administration	Regimen/ Treatment Period	Use
Pembrolizumab	200 mg	Q3W	IV infusion	Day 1 of each 3 week cycle	Experimental

Trial treatment should begin on the day of randomization or as close as possible to the date on which treatment is allocated/assigned.

Trial treatment should be administered on Day 1 of each cycle after all procedures/assessments have been completed as detailed on the Trial Flow Chart (Section 6.0). Trial treatment may be administered up to 3 days before or after the scheduled Day 1 of each cycle due to administrative reasons.

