### 8.1.2 Randomization

This is an open-label randomized trial; therefore, the sponsor, investigator, and subject will know the treatment administered. Two arms will be tested, with each independent assessment. Patients will be randomized to either arm using a computerized randomization program by [name].

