## 8.3 Analyses Plans

### 8.3.1 Analysis Population

We will conduct an intention-to-treat analysis of efficacy. All randomized patients will be evaluated.

For evaluation of safety, we will restrict the arm-specific samples to all patients who have received at least one dose of investigational therapy.

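### PFS and OS are timed from start of treatment, which conflicts with the intention-to-treat analysis of all randomized patients and leaves never-dosed patients without a time zero

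*Combined protocol and SAP*

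**What the plan says.** Section 7.1.4, under Progression-Free Survival, gives the definition: "Progression-free survival (PFS) is defined as the duration of time from start of treatment to time of progression or death". The table in Section 2.3 uses the same origin. Its row for 24-week PFS reads "From initiation of study treatment to time of progression or death, whichever occurs first, assessed up to 24 weeks". Its row for median PFS and OS reads "From initiation of study treatment to the time of death from any cause on study, assessed up to 48 months", and this is the only origin given for OS.

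Section 8.3.1 sets the efficacy population: "We will conduct an intention-to-treat analysis of efficacy. All randomized patients will be evaluated". Only the safety sample is restricted to patients who received a dose. Section 8.3.3 summarises PFS and OS by Kaplan-Meier medians with confidence intervals.

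Two further passages bear on the point. Section 8.1.2 says "This is an open-label randomized trial; therefore, the sponsor, investigator, and subject will know the treatment administered". The note under Table 5.1 says "Trial treatment should begin on the day of randomization or as close as possible" to allocation, with no maximum gap.

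**The concern.** An analysis of all randomized patients needs a starting date that every randomized patient has. The date of first dose is not such a date. Someone who is randomized and then progresses, dies, withdraws or declines before dosing cannot be placed on the PFS or OS time axis as defined, and the plan gives no substitute origin and no censoring rule. For patients who are dosed, a progression between randomization and first dose also falls outside the definition.

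Because the arm is known and only Arm A receives vorinostat (Tables 5.2 and 5.3), a decision not to start can depend on the assignment. The patients left out need not then be balanced between arms. At stake is whether the reported medians and 24-week PFS describe the randomized arms or only those who started, and whether that choice is made before or after the data are seen.

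**Working it through.** **1. Passages side by side.**

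| Item | Origin or population | Section |
|---|---|---|
| PFS | start of treatment | 7.1.4 |
| 24-week PFS | start of treatment | 2.3, row 1 |
| Median PFS, OS | start of treatment | 2.3, row 2 |
| Efficacy population | all randomized | 8.3.1 |
| Safety population | at least one dose | 8.3.1 |
| Primary response rate | randomized to the arm | 8.3.2 |

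The first three rows need a dosing date; the efficacy population does not guarantee one. Nothing in 7.1.4 or 8.3.3 resolves this.

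**2. The plan's own figures.** The plan states no event count, effect size or power for PFS or OS, so there is nothing to reproduce for these endpoints. The response-rate design does reproduce. Arm A has type I error 0.0249 and power 0.904; Arm B has 0.0220 and 0.900. The chance of ending at 46 patients is 0.942 × 0.697 = 0.657 (stated as about 65%). Between-arm power is 72.4% with a two-sided Fisher's exact test at 0.1 (stated as 72.53%). None of these depends on the PFS or OS origin.

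**3. How many patients could be lost.** The documents give no rate, so the number never treated, k, is an assumption.

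| k | of 65 (maximum) | of 46 (most likely) |
|---|---|---|
| 0 | 0% | 0% |
| 1 | 1/65 = 1.5% | 1/46 = 2.2% |
| 3 | 3/65 = 4.6% | 3/46 = 6.5% |
| 5 | 5/65 = 7.7% | 5/46 = 10.9% |

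If each patient independently had probability p of never starting, the chance of at least one is 1 − (1 − p)^n. At p = 1% this is 37% for n = 46 and 48% for n = 65; at p = 2% it is 61% and 73%.

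**4. What the choice of rule does to the summaries.** Suppose a share q of randomized patients is never treated and has an event near time zero, and that treated patients have exponential times with rate λ. The all-randomized median solves (1 − q)·exp(−λt) = 0.5, so t = ln(2(1 − q))/λ. The treated-only median is ln 2/λ. The ratio is ln(2(1 − q))/ln 2. Under the same assumption 24-week PFS is multiplied by 1 − q.

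| q | Median ratio | 24-week PFS ratio |
|---|---|---|
| 2% | ln 1.96 / ln 2 = 0.97 | 0.98 |
| 5% | ln 1.90 / ln 2 = 0.93 | 0.95 |
| 10% | ln 1.80 / ln 2 = 0.85 | 0.90 |

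If the same patients are instead censored at time zero, the Kaplan-Meier estimates do not change. The result therefore depends on a rule the plan does not state.

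**The case against.** The best defence is that little turns on this. Treatment should start on or near the day of randomization, so few events or withdrawals are likely in the gap. PFS and OS are secondary and descriptive. No passage excludes untreated patients, and an analyst could use the randomization date or censor at time zero. All of this stands and limits the importance of the point. It does not remove the conflict: no maximum gap is set, and leaving the rule to the analyst means leaving it until arms and outcomes are known.

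Four stronger readings are tempting, and the documents do not support them.

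- A reader might infer from the pilot, where 6 of 34 patients did not receive pembrolizumab, that a similar share here would lack a time zero. Section 1.5 says all 34 received at least one dose of vorinostat, so all had started study treatment. The pilot gives no rate of never starting.
- A reader might infer that the randomized comparison is invalidated. Section 8.3.3 plans no between-arm test of PFS or OS, and the planned comparison is of response rates.
- A reader might infer that the 24-week primary assessment must be re-anchored too. Section 8.3.2 keeps an untreated patient in the denominator without needing a start date, and no defect is shown there.
- A reader might infer that *on study* in the OS row drops deaths after progression. Sections 3.6 and 6.3.3 plan telephone survival follow-up after progression, and the row runs to 48 months. The wording is loose, but it is not shown to omit deaths.

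**Conclusion.** The conflict is real and lies in the text: the time origin in 2.3 and 7.1.4 cannot be applied to every patient whom 8.3.1 says will be evaluated. That such patients would drop out is a consequence of the definitions, not a written exclusion. The effect is limited to PFS, 24-week PFS and OS; the primary response rate, the sample size and the stopping boundaries are untouched.

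The size cannot be fixed from the documents. It is nil if everyone randomized is dosed without an intervening event. Under the assumed worst case of early events in 2% to 10% of patients, the median falls by 3% to 15% (ratios 0.97 to 0.85). Those figures rest on an exponential model and an assumed q. An imbalance between arms is possible because allocation is open, but the documents give no evidence of its extent.

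**What to change.** - In 2.3, 7.1.4 and 8.3.3, define PFS (including 24-week PFS) and OS from the date of randomization for all randomized patients, analysed in the assigned arm.
- State the rule for never-treated patients: follow them for progression and survival from randomization where possible, and otherwise censor them at the last assessment or contact counted from that date.
- Keep a version timed from first dose, in dosed patients, as a sensitivity analysis only.
- Duration of response keeps its own origin in 7.1.4 (first CR or PR). It shares a row with 24-week PFS in 2.3, so separate the two when editing.
- As a clarification, drop *on study* from the OS row so that it matches the survival follow-up in 3.6 and 6.3.3.

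The cost is a wording amendment and survival contact for any patient who never starts. Recorded times lengthen by the short gap between randomization and first dose. The scan schedule, sample size and decision rules stay as they are.

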## **7.2 Evaluation of Safety**

The safety parameters for this study include all laboratory tests and hematological abnormalities, physical findings, and spontaneous reports of adverse events reported to the investigator by participants.

Toxicity will be assessed according to the NCI CTCAE version 5.0. Safety analyses will be performed for all participants who have received at least one dose of study drug.

## **7.3 Definitions of Adverse Events**

### **7.3.1 Adverse Event**

An adverse event (also known as an adverse experience) is defined as any untoward medical occurrence associated with the use of a drug in humans, whether or not considered drug-related. More specifically, an adverse event (can be any unfavorable and unintended sign (e.g., an abnormal laboratory finding), symptom, or disease temporally associated with the use of a drug, without any judgment about causality. An adverse event can arise from any use of the drug (e.g., off-label use, use in combination with another drug) and from any route of administration, formulation, or dose, including an overdose.

### **7.3.2 Adverse Reaction**

An adverse reaction is defined as any adverse event caused by the use of a drug. Adverse reactions are a subset of all suspected adverse reactions for which there is reason to conclude that the drug caused the event.

### **7.3.3 Suspected Adverse Reaction**

A suspected adverse reaction is defined as any adverse event for which there is a reasonable possibility that the drug caused the adverse event. For the purposes of IND safety reporting, “reasonable possibility” indicates that there is evidence to suggest a causal relationship between the drug and the adverse event. A suspected adverse reaction implies a lesser degree of certainty about causality than an adverse reaction.

#### **7.3.3.1 Unexpected**

An adverse event or suspected adverse reaction is considered *unexpected* if it is not listed in the investigator brochure or package insert(s), or is not listed at the specificity or severity that has been observed, or, if an investigator brochure is not required or available, is not consistent with the risk information described in the general investigational plan or elsewhere in the current application.

“Unexpected,” as used in this definition, also refers to adverse events or suspected adverse reactions that are mentioned in the investigator brochure as occurring with a class of drugs or

as anticipated from the pharmacological properties of the drug, but are not specifically mentioned as occurring with the particular drug under investigation.

Adverse events that would be anticipated to occur as part of the disease process are considered *unexpected* for the purposes of reporting because they would not be listed in the investigator brochure. For example, a certain number of non-acute deaths in a cancer trial would be anticipated as an outcome of the underlying disease, but such deaths would generally not be listed as a suspected adverse reaction in the investigator brochure.

Some adverse events are listed in the Investigator Brochure as occurring with the same class of drugs, or as anticipated from the pharmacological properties of the drug, even though they have not been observed with the drug under investigation. Such events would be considered *unexpected* until they have been observed with the drug under investigation. For example, although angioedema is anticipated to occur in some participants exposed to drugs in the angiotensin-converting enzyme inhibitor class and angioedema would be described in the investigator brochure as a class effect, the first case of angioedema observed with the drug under investigation should be considered *unexpected* for reporting purposes.

### 7.3.3.2 Serious

An adverse event or suspected adverse reaction is considered *serious* if, in the view of either the investigator or sponsor, it results in any of the following outcomes:

- Death
- Life-threatening adverse event
- Inpatient hospitalization or prolongation of existing hospitalization
- A persistent or significant incapacity or substantial disruption of the ability to conduct normal life function
- Congenital anomaly/birth defect

Important medical events that may not result in death are life-threatening or require hospitalization may be considered serious when, based upon appropriate medical judgment, they may jeopardize the participant and may require medical or surgical intervention to prevent one of the outcomes listed in this definition. Examples of such medical events include allergic bronchospasm requiring intensive treatment in an emergency room or at home, blood dyscrasias or convulsions that do not result in inpatient hospitalization, or the development of drug dependency or drug abuse.

#### Serious Adverse Events

A serious adverse event is any adverse event occurring at any dose or during any use of Merck's product that:

- Results in death;
- Is life-threatening;
- Results in persistent or significant disability/incapacity;
- Results in or prolongs an existing inpatient hospitalization;
- Is a congenital anomaly/birth defect;
- Is a new cancer (that is not a condition of the study);

- Is associated with an overdose;
- Is another important medical event

**Note:** In addition to the above criteria, adverse events meeting either of the below criteria, although not serious per ICH definition, are reportable to the Merck in the same timeframe as SAEs to meet certain local requirements. Therefore, these events are considered serious by Merck for collection purposes.

- Is a new cancer (that is not a condition of the study);
- Is associated with an overdose.

Progression of the cancer under study is not considered an adverse event unless it results in hospitalization or death.

Any serious adverse event, or follow up to a serious adverse event, including death due to any cause other than progression of the cancer under study that occurs to any subject from the time the consent is signed through 30 days following cessation of treatment, or the initiation of new anti-cancer therapy, whichever is earlier, whether or not related to Merck product, must be reported within 24 hours to the Sponsor and within 2 working days to Merck Global Safety.

Non-serious Events of Clinical Interest will be forwarded to Merck Global Safety and will be handled in the same manner as SAEs.

Additionally, any serious adverse event, considered by an investigator who is a qualified physician to be related to Merck product that is brought to the attention of the investigator at any time outside of the time period specified in the previous paragraph also must be reported immediately to the Sponsor and Merck.

**SAE reports and any other relevant safety information are to be forwarded to the Merck Global Safety [REDACTED]**

A copy of all 15 Day Reports and Annual Progress Reports is submitted as required by FDA, European Union (EU), Pharmaceutical and Medical Devices Agency (PMDA), or other local regulators. Investigators will cross-reference this submission according to local regulations to the Merck Investigational Compound Number (IND, CSA, etc.) at the time of submission. Additionally, investigators will submit a copy of these reports to Merck & Co., Inc. [REDACTED] [REDACTED] the time of submission to FDA.

All subjects with serious adverse events must be followed up for outcome.

### **7.3.3.3 Life-threatening**

An adverse event or suspected adverse reaction is considered life-threatening if, in the view of either the investigator or sponsor, its occurrence places the participant at immediate risk of death. It does not include an adverse event or suspected adverse reaction that, had it occurred in a more severe form, might have caused death.

### **7.3.4 Recording of Adverse Events**

Refer to the Data Safety Monitoring Plan, located in Appendix 2.

### 7.3.5 Follow-up of Adverse Events

All participants who experience adverse events will be followed with appropriate medical management until resolved or stabilized, as determined by the investigator, or until the initiation of new anti-cancer therapy, whichever occurs first. For selected adverse events for which administration of the investigational product was stopped, a re-challenge of the subject with the investigational drug may be conducted if considered both safe and ethical by the investigator.

### 7.3.6 Adverse Events Reporting

An adverse event is defined as any untoward medical occurrence in a patient, or clinical investigation participant administered a pharmaceutical product and which does not necessarily have to have a causal relationship with this treatment. An adverse event can, therefore, be any unfavorable and unintended sign (including an abnormal laboratory finding, for example), symptom, or disease temporally associated with the use of a medicinal product or protocol-specified procedure, whether or not considered related to the medicinal product or protocol-specified procedure. Any worsening (i.e., any clinically significant adverse change in frequency and/or intensity) of a preexisting condition that is temporally associated with the use of the Merck's product is also an adverse event.

Changes resulting from normal growth and development that do not vary significantly in frequency or severity from expected levels are not to be considered adverse events. Examples of this may include but are not limited to, teething, typical crying in infants and children and onset of menses or menopause occurring at a physiologically appropriate time.

Merck product includes any pharmaceutical product, biological product, device, diagnostic agent or protocol-specified procedure, whether investigational (including placebo or active comparator medication) or marketed, manufactured by, licensed by, provided by or distributed by Merck for human use.

Adverse events may occur during the course of the use of Merck product in clinical trials, or as prescribed in clinical practice, from overdose (whether accidental or intentional), from abuse and withdrawal.

All AEs, SAEs and other reportable safety events that occur after the consent form is signed but before treatment allocation/randomization must be reported by the investigator if the participant is receiving placebo run-in or other run-in treatment, if the event causes the participant to be excluded from the study, or is the result of a protocol-specified intervention, including but not limited to washout or discontinuation of usual therapy, diet, or a procedure.

- All AEs from the time of treatment allocation/randomization through 30 days following cessation of study treatment must be reported by the investigator.
- All AEs meeting serious criteria, from the time of treatment allocation/randomization through 90 days following cessation of study treatment, or 30 days following cessation of study treatment if the participant initiates new anticancer therapy, whichever is earlier must be reported by the investigator.
- All pregnancies and exposure during breastfeeding, from the time of treatment allocation/randomization through 120 days following cessation of study treatment, or 30 days following cessation of study treatment if the participant initiates new anticancer therapy must be reported by the investigator.

- Additionally, any SAE brought to the attention of an investigator at any time outside of the time period specified above must be reported immediately by the investigator if the event is considered to be drug-related.

Investigators are not obligated to actively seek AE or SAE or other reportable safety events in former study participants. However, if the investigator learns of any SAE, including death, at any time after a participant has been discharged from the study, and he/she considers the event to be reasonably related to the study treatment or study participation, the investigator must promptly notify Merck.

All adverse events, whether or not unexpected, and whether or not considered to be associated with the use of the study drug, will be entered into OnCore®, as noted above.

The Investigator will assess all adverse events and determine reportability requirements to the UCSF Data and Safety Monitoring Committee (DSMC) and UCSF's Institutional Review Board (IRB); and, when the study is conducted under an Investigational New Drug Application (IND), to the Food and Drug Administration (FDA) if it meets the FDA reporting criteria.

All adverse events entered into OnCore® will be reviewed by the Helen Diller Family Comprehensive Cancer Center Site Committee on a weekly basis. The Site Committee will review and discuss at each weekly meeting the selected toxicity, the toxicity grade, and the attribution of relationship of the adverse event to the administration of the study drug(s).

All grade(s) 3-5 adverse events entered into OnCore® will be reviewed on a monthly basis at the Site Committee meetings. The Site Committee will review and discuss the selected toxicity, the toxicity grade, and the attribution of relationship of the adverse event to the administration of the study drug(s).

In addition, all suspected adverse reactions considered "serious" entered into OnCore® will be reviewed and monitored by the Data and Safety Monitoring Committee on an ongoing basis and discussed at DSMC meetings, which take place every six weeks.

For a detailed description of the Data and Safety Monitoring Plan for a Phase 2 or 3 Institutional Study at the Helen Diller Comprehensive Cancer Center, please refer to Appendix 2.

